3. STUDY DESIGN

This will be a randomized, efficacy assessor-blinded, parallel group, pilot study of up to 20 subjects with documented UV induced herpes labialis. We will enroll until we have 20 subjects that have expressed a lesion from the induction and complete the treatment period of the study. With the possibility of screen failures and induction failures, we may consent up to 35 patients maximum.

Potential subjects will be assessed during a screening visit that must take place no greater than 2 weeks prior to the Induction visit. During the screening period, subjects that meet all other entry criteria will undergo UV susceptibility testing to determine their individual MED (minimal erythema dose). UV susceptibility testing takes place over two days with exposure to UV light on specified regions on the subject's back followed by an assessment of the exposed areas 24 hours later to identify the MED.

Subjects who have a measurable MED will be allowed to enroll in the study. Each subject will be randomly assigned in a 1:1 ratio to receive either EED or Comparator.

Subjects that do not have a measurable MED will be considered screen failures or may have repeat MED testing with new values.

At the Induction Visit, subjects will undergo UV radiation at a level 3 times their MED. The exposed area of the lip will be marked with indelible ink and a baseline photograph may be taken.

Each subject will then be randomly assigned in a 1:1 ratio to receive either EED or Comparator. Subjects will be dispensed study medication and instructed how to apply it to the exposed area. Dosing of the study product will be done 5 times daily, beginning at the time that a subject first senses the start of the prodromal phase (Day 1). The EED is a clear viscous eye drop, and the Comparator is a white cream substance. Therefore, the subject and principal investigator will be unblinded, and only efficacy assessments will be done by a qualified trained blinded assessor.

Subjects will be given a diary card to record their pain levels (starting at Day 1), progression of lesion development and any unusual symptoms (not normally seen with their outbreaks).

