Patients will be called daily by the study team after their induction visit to determine the start of prodrome. When the patient first senses the prodromal phase, they need to be seen within 24 hours for the Day 1 visit. Patients that do not have prodromal senses within 7 days of the induction will be considered induction failures. Induction failure patients will be asked to return their study drug to the study team.

On Days 1, 3, 5, and 7 the subject will follow up in person or via virtual MyChart visit with blinded assessor during which the subject's diary card will be reviewed and compliance with dosing checked. If the subject has noted any unusual symptoms, these will be discussed with medical personnel to determine if a treatment emergent adverse event has occurred or, if the subject has not started treatment, whether their medical history should be updated. If possible, the lesion will be measured. A photo will be taken of the irradiated area (as marked at the induction visit). More study drug may be dispensed as needed. Most subjects' lesions will have resolved by day 7, and they will end study treatment after 7 full days of

treatment. If lesion has not resolved by day 7, the maximum number of days the patient may use study drug treatment is 10 days. An end of study (EOS) visit will occur as soon as their lesion is healed or Day 10, whichever comes first.

The EOS visit (Day 10) is expected to be the final study visit. EOS will occur when a subject's lesion is fully healed or Day 10 (whichever comes first). A photo will be taken of the irradiated area, the diary card will be carefully reviewed and study product (including empty containers) will be collected. Subjects who developed a lesion that has not yet healed will be given the option to begin taking a prn medication that has been previously prescribed to treat an outbreak.

If an adverse event has occurred but has not resolved by the EOS visit, the subject will be contacted once weekly, and status of the AE noted until such time as the event has resolved.

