4. STUDY TREATMENT

4.1 EDTA Eye Drops

Livionex Inc. has agreed to supply EED. It consists of 2.6% EDTA plus a permeation enhancer (MSM). EED will be packaged in standard dropper bottles and labeled as containing 2.6% EDTA plus MSM as a surfactant.

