4.2 Comparator: Abreva®

Abreva, manufactured by Avinir Pharmaceuticals, is an antiviral agent approved by the FDA for treatment of cold sores. It is packaged in tubes of 2g each.

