6.1.2 Induction Visit

Upon reporting to the clinic for their induction visit, the subject will be randomized to receive either EED or Abreva. The following assessments will then be performed to establish baseline values prior to dosing:

- Review of Medical History and Concomitant Medications for any changes between Screening and Day 1 (Treatment emergent AEs are collected in this study beginning with first instance of dosing. Any unusual symptoms prior to the start of dosing will be recorded, if appropriate, as an update to the subject's medical history).

- Limited Physical Exam to check for any changes between Screening and Day 1(changes in PE after start of dosing will be assessed as possible treatment emergent AEs)

If the subject remains qualified for the study:

- They will be dispensed study product (EED or Abreva) and instructed to use it 5 times daily beginning when they first sense a prodrome or see a lesion (they will be asked to note the day and time of their first dose on their diary card).
- They will be given a diary card and instructed how to complete it. A practice diary completion may be done to ensure that subjects know how to complete the diary.

Subjects will then be discharged from the clinic with an appointment to return on Day 3 via virtual video call. They will be instructed to bring their Diary Card and the tube/bottle of study product that they have received.

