6.1.4 Study Days 3, 5, and 7 Visits

On Days 3, 5, and 7, the subject will present for a follow up appointment in clinic or via virtual video call consisting of:

- Review of the subject’s diary card to identify possible treatment emergent adverse events.
- Assessment of the subject’s pain on a visual analog scale.
- Measurement of the lesion will be taken (if lesion is present).
- Photographs of area exposed to UV radiation may be asked to be taken by subjects and uploaded into their MyChart account. If patients are present in clinic, photographs will be taken by study staff.
- If the subject has experienced a prodrome or lesion they should have started dosing. The study staff will review their dosing compliance and examine the study product tube/bottle. If the subject is not complying with the dosing regimen, the study staff will determine whether non-compliance is serious enough to warrant terminating the subject’s participation. Otherwise, minor non-compliance should be noted, and the subject should be retrained on how to dose themselves.

Once patients reach the Stage 2/3 lesion their lesion may be swabbed for viral culture (HSV PCR). If the patient reaches Stage 2/3 over the weekend, the lesion will not be swabbed. We will reserve this for the first five patients but may continue to do all patients to ensure lesion is in fact a cold sore and not a reaction to the UV radiation.

6.1.5 EOS – End of Study Visit (Day 10 – or after subject’s lesion has fully healed)

An EOS visit will occur after the subject’s lesion has fully healed or Day 10 (whichever comes first), the subject will present to the clinic for a follow up appointment in clinic or via virtual video call consisting of:

- Review of the subject’s diary card to identify possible treatment emergent adverse events. If the subject has an AE that has not resolved by this time, the site staff will explain to the subject that they will be called every week to check on the status of the AE, until it is resolved.
- Assessment of the subject’s pain on a visual analog scale.

- Photographs of area exposed to UV radiation may be asked to be taken by subjects and uploaded into their MyChart account. If patients are present in clinic, photographs will be taken by study staff.

The subject's diary card and all tubes//bottles of study product (empty, partially used or unused) will be collected and the subject will be released from the study.

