7. EFFICACY EVALUATIONS

7.1 Number of subjects that experience prodrome (Stage 1) but do not progress to vesicles (Stage 3) by completion of treatment

The Principal Investigator or his designee will review all photographs taken from Day 1 through the EOS visit against the onset of prodrome date and the date of healing or 7 full days of treatment noted on the subject's diary card. They will then determine the duration of the HSV outbreak (prodrome to healed). This may or may not agree with the subject's assessment of "healed" but should be based on the collective information gathered during the subject's time on study. The blinded assessor will assess the prodrome and/or lesion at every clinic visit starting at day 3. The blinded assessor will only be responsible for the rating of the prodrome and or/lesions. The blinded assessor will not be performing safety evaluations. The unblinded staff will instruct the subject to not talk with the blinded assessor about which treatment they have been using.

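### The plan does not keep the blinded assessor apart from the compliance and product checks made at the same visits, so the blinding behind the primary Stage 3 call is at risk

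*Combined protocol and SAP*

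**What the plan says.** Section 3 explains why blinding is partial: "The EED is a clear viscous eye drop, and the Comparator is a white cream substance". The subject and the principal investigator are therefore unblinded, and efficacy assessment is left to a trained blinded assessor.

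The same section describes the Day 1, 3, 5 and 7 follow-up as taking place in person or "via virtual MyChart visit with blinded assessor during which the subject's diary card will be reviewed and compliance with dosing checked". It adds: "More study drug may be dispensed as needed".

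Other sections divide the work differently. For Days 3, 5 and 7 the synopsis has study staff review the diary, while the blinded assessor rates and measures. Section 6.1.4 says: "The study staff will review their dosing compliance and examine the study product tube/bottle". Section 6.1.3 says the same for Day 1. Section 7.1 restricts the assessor: "The blinded assessor will only be responsible for the rating of the prodrome and or/lesions". It also excludes the assessor from safety evaluations and has unblinded staff tell subjects not to discuss their treatment with the assessor.

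**The concern.** The primary endpoint is whether a subject progresses to Stage 3, a judgement made by looking at the lip. Among those who produce efficacy data, the assessor is the only one the plan describes as blinded, and the trial's title relies on that.

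Section 3 puts this person at the visit where compliance is checked and product may be handed over. If the assessor sees a dropper bottle or a tube, the arm is known, and a borderline call on whether vesicles are present can be influenced by it. No analysis can repair a rating made with knowledge of the arm.

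**Working it through.** The plan states no figure on this point, so the main check is to compare the sections.

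**1. Who does the tasks that could reveal the arm?**
- Section 3, Days 1, 3, 5 and 7: the visit is with the blinded assessor; diary review, compliance check and re-supply occur there; no performer is named.
- Synopsis, Days 3, 5 and 7: study staff review the diary; the assessor rates and measures.
- Sections 6.1.3 and 6.1.4: study staff check compliance and examine the container; the assessor is not mentioned.
- Section 7.1: the assessor only rates.
- Section 10: diary and compliance review and the blinded rating are separate rows, both marked at Day 1, Day 5, Day 7 and end of study.

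The tasks and the rating therefore share visits. Most sections assign them to different people, while Section 3 places them in one encounter with the assessor.

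**2. Would sight of the product identify the arm?** Yes. Section 4.1: "EED will be packaged in standard dropper bottles and labeled as containing 2.6% EDTA plus MSM as a surfactant". Section 4.2, for Abreva: "It is packaged in tubes of 2g each".

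**3. Is the container at the visit?** Yes. Section 6.1.2, about the Day 3 video call: "They will be instructed to bring their Diary Card and the tube/bottle of study product that they have received". Study staff then examine it. At end of study, Section 3 and the synopsis have product collected, and the synopsis and Section 10 have the assessor rate at that visit.

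**4. What keeps it from the assessor?** Section 7.1 gives the limit to rating, the exclusion from safety evaluations and the no-talk instruction. The first two restrict what the assessor does and the third restricts what the subject says. None governs what the assessor sees. No section sets a task order, a separate room or call, or concealment of the container.

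**5. Size.** The target is 20 subjects. One subject classified differently moves an arm's proportion by 1/n, where n is the arm size. Simple randomization does not fix n, so n is an assumption:
- n = 10: 1/10 = 10.0 percentage points
- n = 8: 1/8 = 12.5 points
- n = 12: 1/12 = 8.3 points

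As an illustration with assumed counts not progressing to Stage 3, and the uncorrected form of the χ² test in Section 9.2:
- 3/10 v. 7/10: χ² = 20 × (3×3 − 7×7)² / (10×10×10×10) = 3.20, p = 0.07
- 2/10 v. 7/10: χ² = 20 × (2×3 − 8×7)² / (10×10×9×11) = 5.05, p = 0.02

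One call can change how the comparison reads. This holds for any misclassification in a trial this small. It shows sensitivity and does not estimate bias.

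**The case against.** The strongest reply is that the plan does separate the roles. Section 3 is in the passive voice and gives the assessor none of these tasks. The synopsis and Sections 6.1.3 and 6.1.4 name study staff, Section 7.1 confines the assessor to rating, and Section 10 lists the tasks in separate rows. On this reading the defect is one loosely worded sentence in a pilot that is openly unblinded for subjects and the investigator.

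Much of this stands, and it rules out several stronger readings that a reader might infer:
- *The assessor examines the container under Section 3.* Section 3 does not mention container examination at these visits. Sections 6.1.3 and 6.1.4 do, and they assign it to study staff.
- *The ratings are no longer blind.* That would require the assessor to watch the product tasks, which no section says happens.
- *The no-talk instruction is the only safeguard.* The limit to rating is another.
- *Cream left on the lip reveals the arm.* The documents describe how the products look, not whether residue is visible at a visit.

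The reply does not cover what the assessor can see. Naming who does a task does not keep another person at the same visit, or on the same video call, from seeing it.

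**Conclusion.** The point holds as a conflict between sections and an unprotected blind. Section 3 places the assessor at the visit where compliance is checked and product may be dispensed, other sections give those tasks to study staff, and nothing shields the assessor from recognisable containers. Unblinding is possible under the plan as written; the documents do not establish that it occurs.

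The consequence is 10 percentage points in one arm's primary proportion per subject reclassified, assuming 10 per arm. How often that would happen cannot be derived from the documents.

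A reader might also count 20 × 4 = 80 affected ratings. The documents do not support a firm count. Section 7.1 starts blinded rating at Day 3 (20 × 3 = 60), adding end of study to the four visits gives 20 × 5 = 100, and early healing ends visits sooner. The primary endpoint is in any case one result per subject.

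This is a pilot, but the correction is worth making because the title claims assessor blinding and the loss could not be recovered at analysis.

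**What to change.** Reconcile the synopsis, Sections 3, 6.1.3, 6.1.4 and 7.1 and the Section 10 schedule so that each visit, including end of study, has two steps:

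1. The blinded assessor rates and measures first, with container and diary out of view, then leaves the room or disconnects.
2. Unblinded staff, already in the plan, then review the diary, check compliance, examine the container, and dispense or collect product.

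In the same revision, settle whether blinded rating starts on Day 1 (synopsis, Section 10) or Day 3 (Section 7.1). Label photographs by subject code only. Have the assessor record a guess of treatment at end of study, so that the success of blinding can be reported.

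The cost is protocol wording, a short visit script and a slightly longer visit. Nothing here changes dosing, visit days or sample size, and no handling of the treated lip is proposed. Section 7.1 also has the principal investigator, who is unblinded, or a designee determine outbreak duration from photographs. That is a separate matter, which this change does not resolve.

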	
study medication and instructed how to apply it to the exposed area. When the patient first senses the start of developing a cold sore and applies study medication will be considered Day 1. Dosing of the study product will be done five times daily, beginning at the time that a subject first senses the start of the prodromal phase (Day 1). Subjects will be given a diary card to record their pain levels, progression of lesion development and any unusual symptoms (not normally seen with their outbreaks).
 
Patients will be called daily by the study team after their induction visit to determine the start of prodrome. If after 7 days, the patient does not develop any prodromal senses, the patient will be considered an induction failure.
 
When the patient first senses signs or symptoms of a cold sore, they will have the Day 1 visit conducted within 24 hours. Day 1 visit may be conducted in person or as a MyChart Virtual Visit. Their diary card will be reviewed and if they have experienced a prodrome and/or lesion since the induction visit, their compliance with dosing will be checked. If the subject has noted any unusual symptoms, these will be discussed with medical personnel to determine if the symptoms represent a treatment emergent AE. A photo will be taken of the irradiated area (as marked at the induction visit). The blinded assessor will assess the prodrome and/or lesion and take measurements.
 
On Days 3, 5, and 7, the subject will return to the clinic or follow up via virtual video call for assessment of the irradiated area. Study staff will review the subject diary to determine if the subject is correctly noting the lesion stage. Subjects will have a photo taken of the radiated area and asked to continue with dosing as instructed. Any diary card notation of unusual symptoms in subjects will be reviewed by study staff to determine if the symptoms represent a treatment emergent adverse event. The blinded assessor will assess the prodrome and/or lesion and take measurements. More study product may be dispensed as needed. Most subjects' lesions will have resolved by day 7, and they will end study treatment after 7 full days of treatment. If lesion has not resolved by day 7, the maximum number of days the patient may use study drug treatment is 10 days.
 
The EOS is the final study visit will take place on Day 10. A photo will be taken of the irradiated area, the diary card will be carefully reviewed and study product (including empty containers) will be collected. If subjects reach EOS without full resolution of their lesion(s), they will be given the option to begin taking a prn medication for the remainder of the outbreak. Measurements will be taken. If an adverse event has occurred but has not resolved by the EOS visit, the subject will be contacted once weekly and status noted until such time as the event has resolved. The blinded assessor will assess the prodrome and/or lesion.
 
A Safety follow-up phone call will occur 2 days after the EOS to determine if any new AEs have occurred.
 
Safety will also be evaluated by an independent physician throughout the study. The first independent safety evaluation will be done once 5 subjects

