6.1.3 Day 1 Visit

Day 1 visit will occur within 24 hours of experiencing signs or symptoms of a cold sore. The patient will start applying study drug as soon as they notice signs or symptoms of a cold sore. The subject will present for a follow up appointment in clinic or via virtual video call consisting of:

- Review of the subject's diary card to identify possible treatment emergent adverse events.
- Assessment of the subject's pain on a visual analog scale.
- Measurement of the lesion will be taken (if lesion is present).
- Photographs of area exposed to UV radiation may be asked to be taken by subjects and uploaded into their MyChart account. If patients are present in clinic, photographs will be taken by study staff.
- If the subject has experienced a prodrome or lesion they should have started dosing. The study staff will review their dosing compliance and examine the study product tube/bottle. If the subject is not complying with the dosing regimen, the study staff will determine whether non-compliance is serious enough to warrant terminating the subject's participation. Otherwise, minor non-compliance should be noted, and the subject should be retrained on how to dose themselves.

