9.2 Efficacy Analysis

The proportion of patients with nonulcerative recurrences which do not progress to vesicles (Phase 3) will be compared between treatment groups using a χ^2 test. The episode duration and lesion size parameters will be compared between the treatment groups with a two-sample Student t-test. The time to lesion healing will be assessed using Kaplan-Meier methods. To illustrate the total clinical benefit of EED, an analysis of time to lesion healing and lesion area for all recurrences (i.e., including both ulcerative lesions and nonulcerative recurrences) will be performed as “all lesions.” In this analysis, the impact of prevention of ulcerative lesions will be introduced by assigning zero values to nonulcerative recurrences.

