10. SCHEDULE OF ASSESSMENTS

ASSESSMENT	SCREENING	Induction Visit	Daily after induction visit to Day 1	DAY 1	DAY 5	DAY 7	DAY 10/ EOS	Follow -up phone call (EOS +2 days)
Informed Consent	X							
Medical/HSV History	X	X (med hx only)						
Urine Pregnancy Test (for woman of child bearing potential only)	X							
Limited Physical Exam	X	X						
Concomitant Medications	X	X						X
UV susceptibility test / MED testing	X (exposure)							
MED Reading		X						
Randomization		X						
UV exposure at 3 x MED (cold sore inducing)		X						
Study Product Dispensed		X						
Dosing Begins				X				
Dosing Ends						X		
Collect Study Product (including empty tubes/bottles)							X	
Photograph of irradiated area and lesion may be taken		X		X	X	X	X	X
Measurement of lesion (if possible)				X	X	X	X	X
Dispensing of Diary Card		X						
Review of Diary Card/Dosing compliance				X	X	X	X	
Solicitation of Adverse Events			X	X	X	X	X	X
Rating of lesion by blinded assessor				X	X	X	X	
Phone call to check for prodromal senses			X

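### Lesion size has no stated measuring method at virtual visits, and the protocol contradicts itself on whether it must be measured

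*Combined protocol and SAP*

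**What the plan says.** **Whether size must be measured.** Section 3, covering Days 1, 3, 5 and 7, says "If possible, the lesion will be measured". The Section 10 row reads "Measurement of lesion (if possible". Sections 6.1.3 and 6.1.4 are firm: "Measurement of the lesion will be taken (if lesion is present". The synopsis (Design) is firm too and names the measurer: "The blinded assessor will assess the prodrome and/or lesion and take measurements".

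**At which visits.** The synopsis and Section 10 include measurement at EOS, but the Section 6.1.5 list of EOS procedures omits it. Section 10 has no Day 3 column, although Section 6.1.4 requires a Day 3 measurement.

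**How visits are held.** Section 3: "On Days 1, 3, 5, and 7 the subject will follow up in person or via virtual MyChart visit with blinded assessor". Section 6.1.4: "the subject will present for a follow up appointment in clinic or via virtual video call consisting of". Section 6.1.5, for EOS: "the subject will present to the clinic for a follow up appointment in clinic or via virtual video call consisting of". Section 6.1.2 books the Day 3 return as a video call. The induction visit is in the clinic.

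**Photographs.** The synopsis and Section 3 say that a photograph will be taken. Sections 6.1.3 to 6.1.5 make it optional at remote visits, with the subject taking and uploading it. No section mentions a scale, an image standard or a way to measure by video. The only manual cited (Section 6.1.1) is for the UV and MED testing.

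**What the readings feed.** Section 2.1.2 lists four secondary endpoints, two of which are cumulative lesion area (summed across lesions) and maximum lesion size. Section 9.2: "The episode duration and lesion size parameters will be compared between the treatment groups with a two-sample Student t-test". It assigns zero to nonulcerative recurrences in the all-lesions analysis and has no rule for a lesion that was present but not measured.

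**The concern.** A lesion of unknown distance and angle on a video call cannot be sized unless something of known length is in the picture. Staff who follow the plan as written may measure with an instrument in the clinic, estimate from the screen, ask the subject, or record nothing, and each choice complies with some section. The subject is unblinded (Section 3), so a size that the subject supplies is not a blinded assessment.

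The damage is hard to see afterwards. A maximum taken over fewer readings is equal to or lower than the maximum over all of them, and the dataset does not show which peaks were missed. Attendance does not protect against this: the Per Protocol population (Section 9.1) requires all visits to be attended, and a virtual visit without a measurement is still attended. A pilot is meant to yield usable preliminary estimates, and size estimates that depend on how the visit was held would carry over into the planning of any later trial.

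**Working it through.** The plan gives no figure to reproduce on this point: 20 subjects are stated without an effect size, standard deviation or power. The check has two parts.

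**1. The passages side by side**

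| Place | Measurement | Visit mode |
|---|---|---|
| Synopsis, Design | Firm, by the blinded assessor | Clinic or virtual on Days 1, 3, 5, 7 |
| Section 3 | If possible | Clinic or virtual on Days 1, 3, 5, 7 |
| Section 6.1.3 (Day 1) | Firm if a lesion is present | Clinic or video |
| Section 6.1.4 (Days 3, 5, 7) | Firm if a lesion is present | Clinic or video |
| Section 6.1.5 (EOS) | Not listed | Clinic or video |
| Section 10 | If possible; no Day 3 column; EOS included | Not stated |

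No place gives a measuring method, and none says who decides between clinic and video.

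**2. How much a missed reading could matter (illustration)**

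The lesion course below is assumed; the documents give none.
- Onset is uniform from Day 1 to Day 2.5.
- Size rises linearly to its peak over 1 to 2.5 days, then falls linearly to zero over 2.5 to 5 days (each uniform).
- Readings fall on Days 1, 3, 5, 7 and 10, and each is missed independently with probability q.
- The result is the largest recorded size divided by the true maximum, by simulation.

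In this model no lesion has any size on Day 1 (the earliest onset is Day 1) or on Day 10 (the latest end is 2.5 + 2.5 + 5 = 10). Only Days 3, 5 and 7 carry information.

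| Visits unmeasured (q) | Mean share of true maximum, subjects with a reading | Same, no reading counted as zero |
|---|---|---|
| 0% | 80% | 80% |
| 25% | 72% | 70% |
| 50% | 65% | 53% |

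At q = 50% about 18% of subjects have no size. A hand check agrees: about 60% of simulated lesions are still present on Day 7 and so have three chances of a reading, and nearly all the rest have two, so 0.60 × 0.5³ + 0.40 × 0.5² = 0.075 + 0.100 = 17.5%.

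The 20% shortfall at q = 0 comes from the spacing of visits, not from the wording. What the wording can add is the step down from there. If one arm missed 25 percentage points more visits than the other, the false difference among subjects with a reading would be 80 − 72 = 8 points, or 72 − 65 = 7 points.

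Without the lesion model, the chance that a subject lacks at least one of the four readings on Days 1, 3, 5 and 7 is 1 − (1 − q)⁴: 34% at q = 10%, 68% at q = 25% and 94% at q = 50%.

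**The case against.** The strongest reply is that the procedural sections, which site staff follow, do require measurement, and that the synopsis gives the task to the blinded assessor. On that view the two conditional phrases are loose drafting. A site could also use a scale on video without the protocol saying so; the documents are silent and do not rule it out. This much stands: the plan is inconsistent, not uniformly conditional. It does not supply a remote method, however, and the conditional wording suggests that some visits without a size were expected.

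Several stronger readings are tempting but not supported:
- A reader might infer that the arms will differ, because people who know the treatment choose the visit mode. No section says who chooses, and none gives a reason for the choice to differ by arm.
- A reader might infer that an arm with more virtual visits must look better. A virtual visit need not be an unmeasured one.
- A reader might put the false difference from a 25-point gap at 11 to 16 points (80 − 70 = 10 to 11 depending on rounding; 70 − 53 = 16 to 17). That counts subjects with no reading as having size zero. Section 9.2 assigns zero only to nonulcerative recurrences.
- A reader might think that a skipped visit lowers the cumulative area as a sum over visits. Section 2.1.2 and the synopsis define it as a sum across lesions. An unmeasured lesion leaves that sum incomplete, but no sum over time is defined.

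It is also fair to say that the stakes are limited: the primary endpoint, progression to vesicles, needs no size.

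**Conclusion.** The point holds as one of inconsistency and a missing method. The passages disagree on whether and when size is measured, all visits from Day 1 to EOS may be remote, and nothing makes a remote size comparable with a clinic size. Two of the four secondary endpoints are exposed.

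Under the assumed lesion course, moving from no missed readings to a quarter or a half missed lowers the average recorded maximum from about 80% to 72% or 65% of the true value, and at a half about 18% of subjects have no size. A 25-point imbalance between arms would shift the comparison by about 7 to 8 points, but the documents give no ground to expect one. These figures rest on the assumed timing and on independent misses; they show direction and rough scale and do not forecast this trial. It should be corrected because the correction is cheap, but it does not threaten the primary comparison.

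**What to change.** 1. Give each subject paper scale strips with the diary card. Require an image with the strip beside the lesion at every visit from Day 1 to EOS, clinic or virtual, with Day 3 and EOS included.
2. Have the existing blinded assessor read size from that image by one method at all visits.
3. Delete *if possible* in Section 3 and in the Section 10 row, add measurement to the Section 6.1.5 list, add a Day 3 column to Section 10, and make the photograph wording in Sections 6.1.3 to 6.1.5 firm, so that all agree with the synopsis.
4. Record the visit mode, so that sizes can also be shown by mode.
5. State in Section 9.2 that a lesion present but unmeasured is missing, not zero, and keep zero for nonulcerative recurrences only.

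The cost is a few strips per subject, one instruction at induction, and slightly more photographing and reading. No visits or staff are added, and virtual visits remain possible.
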